#### 8.3. Sample Size considerations

This study is designed to show superiority of nutritional therapy compared to "appetite-guided" standard care regarding the composite primary endpoint. Our hypothesis is that early nutritional therapy will reduce mortality and morbidity within a follow up period of 30 days after the index hospitalization. From preliminary observational data collected during the TRIAGE pilot study, we estimate that 40% of the target patient population (NRS ≥3 points and LOS ≥5days) will reach the primary endpoint within 30 days (10% mortality, 5% ICU admission from the hospital ward, 15% complications, 10% functional decline with 10% reaching more than 1 endpoint). We hypothesize that our nutritional intervention will decrease this risk by an absolute number of 6% (relative decrease of 15%), i.e., from 40% to 34%. For a comparison of two independent binomial proportions using Pearson's Chi-square statistic with a Chi-square approximation with a two-sided significance level of 0.05, a sample size of 1'359 per group achieves a power of at least 0.9 when the proportions are 0.4 and 0.34.

Thus, a total number of 2000-3000 patients will provide the study with a power of 78-90% to detect a 15% relative decrease in the risk to reach the primary endpoint. The table below shows sample sizes for different assumptions regarding effectiveness of our intervention and power.

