Outcome(s):	The primary composite endpoint is combined adverse outcome within 30 days defined as (a) all-cause mortality, (b) admission to the intensive care unit from the medical ward, (c) major complications, (d) unplanned hospital readmissions and (d) decline in functional outcome from admission to day 30 assessed by Barthel's index (-10%). Secondary endpoints include (a) each single component of the primary endpoint (b) short-term nutritional and functional outcomes from inclusion to day 10 or hospital discharge; (c) hospital outcomes; (d) 30-day and 180-day outcomes (e) Other safety endpoints including adverse gastrointestinal effects associated with nutritional therapy assessed daily until hospital discharge.	
Study design:	Randomized controlled trial	
Inclusion / Exclusion criteria:	Unselected adult medical inpatients at risk of undernutrition [NRS≥3 points] and an expected hospital stay of ≥5 days who are willing to provide informed consent will be included. We will exclude patients in critical care or post-operative state, unable to swallow, at long-term need for parenteral/enteral nutrition, in terminal condition, pregnant, with acute pancreatitis or acute liver failure, with anorexia nervosa, that were earlier included into the trial	

Measurements and procedures:	Patients in the intervention group will receive individualized nutritional therapy to reach nutritional targets (caloric, protein, micronutrients, other) based on a predefined nutritional strategy. In control patients, according to patients' appetite, standard hospital nutrition will be served. Nutritional therapy may be started in control patients, if any sort of swallowing disorders develops or if patients need to be prepared for operation. All patients will be re-assessed daily during the hospital stay for nutritional intake and nutritional therapy may be escalated every 24-48 hours (food fortification, oral supplements, enteral, parenteral nutrition) if targets are not met (at least 75% of targets).		
Study Product / Intervention:	Different nutritional products (oral nutritional supplements, enteral nutrition, parenteral nutrition) to reach nutritional targets		
Control Intervention:	Usual care;		
Number of Participants with Rationale:	The inclusion of 2000-3000 patients will provide 78-90% power to detect a reduction in the primary endpoint of 15% (from 40% to 34%)		

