# 8.2. Statistical approach

Detailed methodology for summaries and statistical analyses of the data collected in this study will be documented in a statistical analysis plan. The statistical analysis plan will be finalized before database closure.

Briefly, a consort diagram will be reported including all screened patients, patients lost to follow up and patients included in the final analyses. Primary and secondary endpoints will be compared between trial arms in the overall ITT population and within predefined subgroups as discussed below. All outcomes will be analyzed in an uncorrected manner as well as jointly corrected for the main risk factors (Barthel's index at baseline, study center and initial NRS categories). For our primary analysis, we will compare the two arms with a chi-square test and we will also estimate effect size with a logistic regression model reporting unadjusted and adjusted odds ratios (OR) and corresponding 95% confidence intervals (CIs).

We will do different predefined subgroup analyses by including interaction terms in the regression models to test for effect modification by important baseline factors. Specifically, we will look at patients age (<60, 60-75, >75 years), gender, risk for undernutrition stratified according to initial NRS (3, 4, >4 points), BMI (<20, 20-25, >25-30, >30), main medical diagnosis (systemic infection, heart failure, acute renal failure, gastro-intestinal disease, tumor), comorbidities (diabetes, chronic renal failure).

For the analysis of functional outcome (defined by Barthel's index) we will use a non-parametric Wilcoxon rank sum test to compare Barthel's index at day 30 between randomization arms. However, to adjust for additional variables, we will also fit a multivariate linear model including Barthel's index at baseline, study center and initial NRS to estimate effect size and 95% confidence intervals (95%Cls). If needed, data will be transformed as appropriate (e.g., log transformation). Moreover, we will assess the progression of Barthel's index over time (i.e. admission, day 8, day 30) using a linear mixed model approach to account for the repeated measurements per patient.

A similar approach will be used for all other secondary endpoints where we will use chi-square tests / logistic regression analysis for binary outcomes, Wilcoxon rank sum test / linear models for continuous outcomes and log-rank test / cox regression for time-to-event data as appropriate.

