# Sample size considerations in regard to the primary endpoint

Frequency of 1° EP intervention group	Frequency of 1° EP control group	Difference control/intervention groups	Power	Patients per group
0.4	0.36	-10%	0.8	2311
0.4	0.36	-10%	0.85	2643
0.4	0.36	-10%	0.9	3093
0.4	0.34	-15%	0.8	1016
0.4	0.34	-15%	0.85	1162
0.4	0.34	-15%	0.9	1359
0.4	0.32	-20%	8.0	564
0.4	0.32	-20%	0.85	645
0.4	0.32	-20%	0.9	755

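### Section 8.3 and the synopsis give 90% power at 3000 patients; the protocol's own test and rates give about 93%, and 90% belongs to 2718

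*Protocol*

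**What the plan says.** Protocol section 8.3 plans the primary comparison on "Pearson's Chi-square statistic with a Chi-square approximation", "with a two-sided significance level of 0.05". It assumes an effect described as an "absolute number of 6% (relative decrease of 15%), i.e., from 40% to 34" per cent. From this it derives that "a sample size of 1'359 per group achieves a power of at least 0.9 when the proportions are 0.4 and 0.34". The next sentence draws a conclusion for the range of sizes under consideration: "a total number of 2000-3000 patients will provide the study with a power of 78-90" per cent. The synopsis carries the same range: "The inclusion of 2000-3000 patients will provide 78-90% power".

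The table that follows 8.3 lists 1016, 1162 and 1359 per group for 80%, 85% and 90% power at 0.40 against 0.34, which is 2032, 2324 and 2718 in total. Its first column is headed "Frequency of 1° EP intervention group" and holds the value 0.4, while the lower rate stands under the control group.

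Section 8.2 confirms the test for the primary analysis: "we will compare the two arms with a chi-square test". No continuity correction is mentioned in either section. Section 8.3 states no allowance for losses, and section 8.1 puts all randomised patients in the primary analysis set.

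**The concern.** Read as pairs, the two ends of the range attach 78% to 2000 patients and 90% to 3000. One sentence earlier, 90% is attached to 2718. Both cannot be the result of the same calculation, yet the range is presented as following from it.

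The protocol fixes no single sample size, so the range is its summary of what different totals would buy. The synopsis gives only the range, without the 1359 per group or the table. Someone who reads the synopsis alone sees a wrong power for the larger total and has nothing there to check it against.

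**Working it through.** **Inputs.** Control rate 0.40, intervention rate 0.34, two-sided alpha 0.05 and uncorrected Pearson chi-square (all 8.3); 1:1 allocation (4.3). The difference is 0.06 and the mean rate 0.37.

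- Null variance term: 2 × 0.37 × 0.63 = 0.4662
- Alternative variance term: 0.40 × 0.60 + 0.34 × 0.66 = 0.4644

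**Step 1: reproduce the protocol's own size.** Per group,

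n = [1.960 × √0.4662 + z(power) × √0.4644]² / 0.06²

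For 90% power: (1.3382 + 1.2816 × 0.6815)² / 0.0036 = (2.2116)² / 0.0036 = 1358.6, so 1359 per group. For 80% power the same formula gives 1016. All nine sizes in the table reproduce exactly, so this is the method behind it.

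**Step 2: power at the stated totals.**

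Power = Φ{[0.06 − 1.960 × √(0.4662/n)] / √(0.4644/n)}

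- n = 1000: (0.06 − 0.04232) / 0.02155 = 0.820, power 79.4%
- n = 1359: (0.06 − 0.03630) / 0.01849 = 1.282, power 90.0%
- n = 1500: (0.06 − 0.03455) / 0.01760 = 1.446, power 92.6%

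**Step 3: look for a variant that yields both printed ends.**

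| Method | 2000 patients | 3000 patients |
|---|---|---|
| Printed in protocol | 78% | 90% |
| Pearson, pooled variance | 79.4% | 92.6% |
| Pearson, unpooled variance | 79.5% | 92.6% |
| Pearson, exact enumeration | 79.3% | 92.6% |
| Continuity-corrected, approximate | 78.1% | 92.0% |
| Continuity-corrected, exact enumeration | 78.0% | 92.1% |
| Pearson, 5% loss | 77.3% | 91.3% |
| Pearson, 9.4% loss | 75.4% | 90.0% |

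A continuity correction explains 78% at 2000 but leaves 3000 at 92%. It also conflicts with the table: with the correction, 1359 per group gives 89.3%, and 90% would need 1392 per group.

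A loss of 9.4% turns 3000 into 2718 (3000 × 0.906) and so explains the 90%. The same loss turns 2000 into 1812, where power is 75.4%. A one-sided test moves further away, with 87.2% and 96.1%. None of the variants tried gives 78% and 90% together.

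**Step 4: size of the gap.** At 2000 the printed figure is 79.4 − 78 = 1.4 points low. At 3000 it is 92.6 − 90 = 2.6 points low.

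**Table headings.** The text of 8.3 and the synopsis both have the rate falling from 40% to 34% with the intervention. The table as headed has the intervention group at 0.4 and the control group lower. With a two-sided test and equal groups the sizes are the same either way.

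**The case against.** The best defence is that the range is a rounding of the exact result. Section 8.3 speaks of power of at least 0.9 at 1359 per group, 2718 was taken up to 3000, and 90% was carried over as the level assured. On that reading nothing false is promised, since 3000 patients do give at least 90%. Part of this stands: the error is on the safe side and its origin is easy to guess. But the printed range does not say at least. It pairs two sizes with two powers, and the second pair is not what the calculation gives.

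Three stronger readings are tempting, and the document does not support them.

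- A reader might infer that both ends are wrong. At 2000 the gap is 1.4 points and the printed 78% agrees with a continuity-corrected test, so it can pass as a conservative figure.
- A reader might infer that this sentence is all the protocol offers on size and power. The sentence before it and the table give the correct mapping, with three totals inside the range.
- A reader might infer that the trial would enrol 3000 − 2718 = 282 patients more than it needs for 90%. Nothing in the protocol makes 3000 a requirement for 90% power. Section 15 treats 3000 as an ambitious recruitment aim and does not tie it to that figure.

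**Conclusion.** The upper end of the stated range is wrong as written, in 8.3 and in the synopsis. By the protocol's own method 3000 patients give about 93% power, and 90% belongs to 2718. The lower end is slightly conservative and would not merit comment alone, but the two ends share no common basis among the methods and loss rates tried.

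The correction is minor. Power is understated, the trial is adequately powered under its assumptions, and the test, alpha, effect and table sizes are unaffected. The figures take the 40% and 34% rates as given and assume equal groups, no continuity correction and outcome data on everyone randomised. The reversed table headings are a separate clerical matter and add no weight to this point.

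**What to change.** In section 8.3 and in the synopsis, replace the range by three matched pairs: *2000, 2718 and 3000 patients give about 79%, 90% and 93% power (Pearson chi-square without continuity correction, two-sided 0.05, 40% v 34%).* If a continuity correction or an allowance for losses was intended, state it and recompute both ends with it.

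In the same edit, swap the first two column headings of the sample size table so that 0.4 stands under the control group, as in the text.

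The cost is two sentences and two headings. No patients are added, and neither the test nor any tabulated sample size changes.

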# Sample size considerations in regard to the primary endpoint

Frequency of 1° EP intervention group	Frequency of 1° EP control group	Difference control/intervention groups	Power	Patients per group
0.4	0.36	-10%	0.8	2311
0.4	0.36	-10%	0.85	2643
0.4	0.36	-10%	0.9	3093
0.4	0.34	-15%	0.8	1016
0.4	0.34	-15%	0.85	1162
0.4	0.34	-15%	0.9	1359
0.4	0.32	-20%	8.0	564
0.4	0.32	-20%	0.85	645
0.4	0.32	-20%	0.9	755

# 8.4. Pilot phase and trial duration:

Prior to start of this complex trial, we will do a 3-6 month pilot to study feasibility. During this time period we will validate all trial related materials (e.g. case report forms, patient and health care worker information sheets) and test feasibility of our intervention. Based on these results we may make last-minute protocol enhancements. Thereafter, we include study centers in a stepwise fashion for a maximal total enrollment period of 3 years.

# 9. Trial-specific preventive measures and duties

# 9.1. Trial monitoring

In accordance with applicable regulations and good clinical practice (GCP), monitors will periodically contact the different sites, including on-site visits. The extent, nature and frequency of on-site visits will be based on enrolment rate, the quality of the documents provided by the site, consistency of follow-up of the patients according to this protocol.

During these contacts, the monitor will check and assess the progress of the trial, review trial data collected, conduct source document verification and identify any issues and address their resolution.

This will be done in order to verify that the data are authentic, accurate, and complete, that safety and rights of subjects are being protected and that the trial is conducted in accordance with the currently approved protocol (and any amendments), GCP, and all applicable regulatory requirements.

The investigator agrees to allow the monitor direct access to all relevant documents and to allocate his/her time and the time of his/her staff to the monitor to discuss findings and any relevant issues. In addition to contacts during the trial, the monitor will also contact the site prior to the start of the trial to discuss the protocol and data collection procedures with site personnel.

#### 9.2. Adverse outcome

An adverse event in a subject is defined as any untoward occurrence of any unfavorable and unintended clinically relevant medical sign, symptom, or disease temporally associated with the study which must not necessarily have a causal relationship with the study procedure. All adverse events of category III or more according to Common Terminology Criteria for Adverse Events (CTCAE) v4.0 will be recorded. Adverse events will be monitored for every subject participating in the study and attributed to the study procedures / design by the study investigators. Any serious unexpected adverse event will be categorized into the following categories:

#### Unrelated

There is no evidence of any causal relationship.

# Unlikely

There is little evidence to suggest there is a causal relationship (e.g. the event did not occur within a reasonable time after administration of the IMP). There is another reasonable explanation for the event (e.g. the participant's clinical condition, other concomitant treatment).

#### **Possible**

There is some evidence to suggest a causal relationship (e.g. because the event occurs within a reasonable time after administration of the IMP). However, the influence of other factors may have contributed to the event (e.g. the participant's clinical condition, other concomitant treatments).

#### **Probable**

There is evidence to suggest a causal relationship and the influence of other factors is unlikely.

#### Definitely

There is clear evidence to suggest a causal relationship and other possible contributing factors can be ruled out.

# Not assessable

There is insufficient or incomplete evidence to make a clinical judgment of the causal relationship.

The following grade levels will be used in defining the severity of adverse events:

# Adverse Event (AE):

Any untoward medical occurrence in a clinical trial subject which does not necessarily have a causal relationship with this treatment. An AE can therefore be any unfavorable and unintended sign (including an abnormal laboratory finding), symptom, or disease temporally associated with the trial, whether or not considered related to the trial.

# Adverse Reaction (AR):

All untoward and unintended responses to the intervention judged by either the reporting investigator or the sponsor as having a reasonable causal relationship to the trial. The expression reasonable causal relationship means to convey in general that there is evidence or argument to suggest a causal relationship.

# **Unexpected Adverse Reaction (UAR):**

An AR, the nature or severity of which is not consistent with the applicable product information (e.g. investigator's brochure for an unapproved investigational product or summary of product characteristics (SmPC) for an authorized product). When the outcome of the adverse reaction is not consistent with the applicable product information this adverse reaction should be considered as unexpected. Side effects documented in the IB or SmPC which occur in a more severe form than anticipated are also considered as being unexpected.

# Serious Adverse Event (SAE) or Serious Adverse Reaction:

Any untoward medical occurrence or effect that at any dose results in death, is life-threatening, requires hospitalization, or prolongation of existing hospitalization, results in persistent or significant disability or incapacity or is a congenital anomaly or birth defect. In this context, the term life threatening refers to an event in which the trial participant was at immediate risk of death at the time of the event; it does not refer to an event, which might have caused death if it were more severe.

# **Suspected Unexpected Serious Adverse Reaction (SUSAR):**

Any suspected adverse reaction related to an IMP that is both unexpected and serious.

All adverse events must be followed until resolution, until the condition stabilizes, until the event is otherwise explained, or the subject is lost to follow-up. The investigator is responsible to ensure that follow-up includes any supplemental investigations that may be indicated to completely evaluate the nature and/or causality of the adverse event. This may include additional laboratory tests or

investigations, histo-pathological examinations, or consultation with other health care professionals, and reports.

# **Reporting of Serious Adverse Events**

All SAEs and SUSARs must be reported to the sponsor within 24 - 48 hours of knowledge. For documentation a trial specific SAE report form provided by the sponsor must be filled in. Collection of complete information concerning SAEs is extremely important. If not available at time of the initial report, detailed information about SAEs should be given in the follow-up report together with all relevant documentation e.g. laboratory and hospital discharge reports.

The sponsor will review these cases. In case of SUSAR, these cases will be reported to the DSMB. SAE will be reported annually to the ethics committee and to the reporting authorities; life threatening SUSAR or SUSAR resulting in death will be reported to the ethics committee and to the reporting authorities (Switzerland: Swissmedic, Safety of Medicines Division; [contact]) within 7 days, all other SUSAR within 15 days of knowledge, according to local law.

The study coordinating centre may request that the investigators perform or arrange for the conduct of supplemental measurements and/or evaluations. If a subject dies during participation in the trial, the study coordinating centre should be provided with a copy of any post-mortem findings, including histopathology.

# 10. Duties on the part of the investigator

The investigators and institutions will permit study related monitoring visits, audits, IEC reviews, and regulatory inspections, and provide direct access to all source data.

Source data are all information, original records of clinical findings, observations, or other activities in this clinical trial necessary for the reconstruction and evaluation of the trial.

In accordance with applicable regulations and good clinical practice (GCP), monitors will periodically contact the site, including on-site visits. The extent, nature and frequency of on-site visits will be based on enrolment rate, the quality of the documents provided by the site, consistency of follow-up of the patients according to this protocol.

During these contacts, the monitor will check and assess the progress of the trial, review trial data collected, conduct source document verification and identify any issues and address their resolution.

This will be done in order to verify that the data are authentic, accurate, and complete, that safety and rights of subjects are being protected and that the trial is conducted in accordance with the currently approved protocol (and any amendments), GCP, and all applicable regulatory requirements.

The investigator agrees to allow the monitor direct access to all relevant documents and to allocate his/her time and the time of his/her staff to the monitor to discuss findings and any relevant issues.

In addition to contacts during the trial, the monitor will also contact the site prior to the start of the trial to discuss the protocol and data collection procedures with site personnel.

#### 11. Ethical considerations

The study will be approved by the ethics committees of the participating hospitals.

This study will be conducted in compliance with the protocol approved by the IEC, and according to ICH-Good Clinical Practice standards. No deviation from the protocol will be implemented without prior review and approval of the IEC except where it may be necessary to eliminate an immediate hazard to a research subject. In such case, the deviation will be reported to the IEC as soon as possible. All enrolled patients will be asked to give written informed consent. In patients, in which "informed consent" is not feasible due to dementia or their acute medical condition, patients' next to kin can sign an assent form to state the presumptive will of the patient. In case, next of kin are not readily available, a treating physician – who must not be involved in the study – have to certify that there are no objections for inclusion in the study from his point of view. Only after these informed consent procedures the patient can be included in the study.

Importantly, despite strong associations between malnutrition and adverse clinical outcome, we believe that is ethically acceptable that the control group receive usual care treatment because there is uncertainty about the effectiveness and safety of nutritional therapy in this patient population. This important subject has been discussed among national experts in the field (i.e., collaborators) who all agree to this practice. This is also in accordance with a recent Swiss consensus ethical statement pointing out that "intake of standard food and fluids is a basic right of any patients", yet any sort of nutritional therapy must be viewed as a therapeutic measure and must therefore fulfill all criteria for such including proof of clinical effectiveness, safety and cost-effectiveness). For our patient population, such proofs is still missing and the main aim of this trial.

